7.3 Secondary Efficacy Endpoint Analysis

7.3.1 Investigator's Assessment of Clinical Success

The number and percentage of subjects with an (overall) investigator's assessment of clinical success, clinical failure and indeterminate response at the EOT, PTE, and FFU visits (ITT, micro-ITT, and CE populations; by definition subjects in the CE population cannot have an indeterminate response) will be determined by treatment group. Exact 95% confidence intervals will be determined for the point estimates of the clinical success rates in each treatment group and for difference from nitrofurantoin (omadacycline - nitrofurantoin).

[figure not shown]
Reasons for investigator assessment of clinical failure and indeterminate at EOT and for overall assessment at PTE and FFU visits will be tabulated.

7.3.2 Per-Subject Microbiological Response

The per-subject microbiological (overall) response at the EOT and PTE Visits in the micro-ITT, ME-EOT and ME-PTE populations will be determined to support the clinical findings.

The number and percentage of subjects classified with a favorable (eradication) and unfavorable (persistence and indeterminate) microbiological response (by definition, indeterminates are excluded from the ME population) will be tabulated for both treatment groups. Exact 95% confidence intervals will be determined for the point estimates of the favorable microbiologic outcome rates in each treatment group and for difference from nitrofurantoin (omadacycline - nitrofurantoin).

Concordance of microbiological outcome with clinical outcome at EOT and PTE visits for the micro-ITT and ME populations will be provided.

7.4 Exploratory Analyses

7.4.1 UTI signs and symptoms assessment

[figure not shown]
Results of the UTISA questionnaire will be summarized in the ITT, micro-ITT, and CE populations. Summaries will be based on the available data; no imputations will be applied to missing values.

[figure not shown]
Shifts from Baseline will be summarized separately for severity scores and bothersome scores at each post-Baseline assessment, daily up to EOT (including self-completion by subject at home on Days 2, 4 and 6), PTE and at FFU.

[figure not shown]
Total scores for severity and bothersomeness will be summarized by time point using descriptive statistics, for both the actual values and the change from baseline.

[figure not shown]
Frequency of subjects with resolution of all clinical UTI symptoms, subjects with no worsening symptoms, and subjects with the absence of new UTI symptoms will be presented.

[figure not shown]

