Note: In all cases, if an estimated start date is after a complete stop date, use the first day of the stop date month. Similarly, if the estimated stop date is before a complete or imputed start date, use the last day of the start day month.

In all cases, if it cannot be determined if the adverse event occurred prior to or after the first dose of test article, the adverse event should be defined as treatment emergent.

- If no value can be obtained for all other times for events and assessments occurring after randomization, the time will not be imputed but will remain missing.
- The severity and causality assessment for AEs cannot be missing. Missing data will be queried for a value. The highest severity and most related causality should be used if query is missing. If query will return missing, then the highest severity and most related causality will be used for the purpose of summaries.
- If the reported value of a clinical laboratory parameter cannot be used in a statistical summary table (eg, a character string is reported for a parameter of the numerical type), a coded value must be appropriately determined and used in the statistical analyses. A

value or lower limit of normal range (eg will be calculated as 99.99% of the value if it is reported as “<” (eg <5 will be converted to $5 \times 0.99 = 4.9995$). The upper normal range of a value will be converted to 100.01% if it is reported as “>” (eg >7 will be converted to $7 \times 1.001 = 7.007$). However, the actual values as reported in the database will be presented in data listings.

- Prior and Concomitant Medication Start Date Imputation will be imputed according to table in [Appendix 4 Concomitant Medication Start Date Imputation](#).

2. Efficacy Data

- Analysis of efficacy data will be based on the available data, unless otherwise stated.
- Missing data for clinical and microbiological outcomes will be denoted “indeterminate” unless otherwise stated.
- Missing microbiological outcomes at EOT will be imputed by last day of test article intake.
- The Overall Clinical Response at PTE and FFU visits are derived based on the “worst case scenario” to accommodate for missing visit assessments and intercurrent events (eg rescue medication at EOT visit). Similar imputations were applied to microbiological response endpoints. Details are described in [Section 7](#).
- UTISA data for bothersome score will be imputed with score of 0 for each question for which severity is answered “Did not have”.

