- Missing UTISA responses at baseline will be imputed with Day 1 responses.

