7.1.2.3 Other microbiological endpoints

7.1.3 UTI Signs and Symptoms Assessment

Subject assessment of UTI signs and symptoms severity will be collected at Screening, and daily through EOT (including self-completion by subject at home on Days 2, 4 and 6), at PTE and at FFU via the UTISA questionnaire.

The UTISA is a subject completed, 14-item questionnaire that assesses the levels of ‘severity’ and ‘bothersomeness’ for each of the seven most frequently reported symptoms and signs of UTI:

- Frequency
- Urgency
- Pain/burning on urination
- Incomplete voiding
- Pain in pelvic area
- Low back pain

- Blood in urine

[figure not shown]
Each item has a Likert-type response scale, the ‘severity’ item response options being ‘did not have’, ‘mild’, ‘moderate’, ‘severe’, scored 0–3; and the bothersomeness item response options being ‘not at all’, ‘a little’, ‘moderately’, ‘a lot’, scored 0–3.

Total scores of the 7 items for the severity of signs and symptoms scores and total scores for the 7 items related to the bothersomeness will be calculated for each subject and visit. The total scores for severity and bothersomeness will be between 0 and 21. The total score 0 is indicating the least severity of signs and symptoms and a total score of 21 is indicating the worst severity. For bothersomeness, the total score 0 is indicating the least bothersome score and a total score of 21 is indicating the most bothersome score.

The bothersomeness questions are only answered if the subject reported presence of the sign/symptom, otherwise this answer is omitted by design.

For calculating the individual total subject score by timepoint for both sub-scales, the scores of non-missing item scores are summed up and divided by the number of non-missing items and then multiplied by 7. If less than 4 items are answered for each sub-scale, the total score is set to ‘missing’ for the sub-scale of the subject.

Frequency of subjects with resolution of all symptoms, without occurrence of new symptoms (in comparison to baseline), and no worsening of baseline symptoms will be provided by timepoint.

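### The SAP's rules for the exploratory UTISA bothersomeness total conflict, and followed without imputation they remove subjects with three or fewer symptoms and scale up those with four to six

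*SAP*

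**What the plan says.** Three sections of the SAP bear on the score.

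- **Section 7.1.3 (scoring).** There are seven severity items and seven bothersomeness items, each scored 0 to 3, so each total runs from 0 to 21. On the skip pattern: "The bothersomeness questions are only answered if the subject reported presence of the sign/symptom, otherwise this answer is omitted by design". On the total: "the scores of non-missing item scores are summed up and divided by the number of non-missing items and then multiplied by 7". On the minimum: "If less than 4 items are answered for each sub-scale, the total score is set to" missing.
- **Section 5.1.2 (missing data).** "UTISA data for bothersome score will be imputed with score of 0 for each question for which severity is answered" as symptom not present. Also: "Missing UTISA responses at baseline will be imputed with Day 1 responses".
- **Section 7.4.1 (analysis).** The UTISA summaries use the available data, and "no imputations will be applied to missing values". The totals are described by time point, as actual values and as change from baseline.

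No section says which rule takes precedence.

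**The concern.** Section 5.1.2 calls both of its UTISA rules imputation, and 7.4.1 rules imputation out for the same data. A programmer working from the analysis section therefore has textual support for leaving skipped bothersomeness items blank.

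The blanks are not random. They arise exactly where a symptom is absent, so they multiply as patients recover. With the proration and the four-item minimum of 7.1.3, blanks change the meaning of the score. It becomes the average bother per remaining symptom, available only for subjects who still have at least four symptoms. The bothersomeness summaries of a dose-finding trial would then say little about recovery, and two programmers reading different sections would produce different tables.

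**Working it through.** **Inputs.** Seven items, each 0 to 3; proration over non-missing items; minimum of four answered items; skip when the symptom is absent (all SAP 7.1.3). Zero rule (5.1.2). No imputation (7.4.1).

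**The SAP's own range.** 7 × 0 = 0 and 7 × 3 = 21, as stated.

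**Two scorings.** Let k be the number of symptoms present, with every applicable question answered, and S the sum of the k bothersomeness answers.

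- Zero rule (5.1.2): total = S, since the other 7 − k items are 0.
- No imputation (7.4.1 with 7.1.3): missing if k < 4, otherwise (S / k) × 7, which is S × 7/k.

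| Symptoms present | Zero rule, each rated 1 | No imputation, each rated 1 | Zero rule, each rated 3 | No imputation, each rated 3 | Multiplier 7/k |
|---|---|---|---|---|---|
| 0 | 0 | missing | 0 | missing | – |
| 1 to 3 | 1 to 3 | missing | 3 to 9 | missing | – |
| 4 | 4 | 7 | 12 | 21 | 1.75 |
| 5 | 5 | 7 | 15 | 21 | 1.40 |
| 6 | 6 | 7 | 18 | 21 | 1.17 |
| 7 | 7 | 7 | 21 | 21 | 1.00 |

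Without imputation the number of symptoms drops out of the score: four symptoms rated 3 reach the scale maximum, the same as seven. The multiplier has no effect if every answered item is 0. None of this table needs an assumption about the trial population.

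**Baseline.** Inclusion criterion 3 (protocol 6.2) requires two of four symptoms. An eligible subject reporting only two or three UTISA symptoms would have no baseline bothersomeness total, and so no change from baseline.

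**The zero rule alone leaves a gap.** Section 7.1.3 prorates over *non-missing* items but sets the minimum on items *answered*. A zero-filled item is non-missing, yet the subject did not answer it. If it does not count as answered, totals for k of 4 or more are correct, but those for k of 0 to 3 are still missing.

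**Illustration only.** Assume each symptom is present independently with probability q and that bother is 1, 2 or 3 with equal chance (mean 2). Neither assumption comes from the documents. The missing share is 1 − P(K ≥ 4) for K binomial (7, q). The zero-rule mean over all subjects is 7 × q × 2. The no-imputation mean is 7 × 2 = 14 at any q. The last column comes from a simulation of 400,000 subjects per row.

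| q | Total missing if k < 4 | Zero rule, all subjects | No imputation, remaining subjects | Zero-filled but not counted as answered, remaining subjects |
|---|---|---|---|---|
| 0.8 | 3.3% | 11.2 | 14.0 | 11.39 |
| 0.5 | 50% | 7.0 | 14.0 | 9.19 |
| 0.2 | 96.7% | 2.8 | 14.0 | 8.32 |
| 0.1 | 99.7% | 1.4 | 14.0 | 8.05 |

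If 'not at all' (0) is also allowed, with 0 to 3 equally likely, the no-imputation mean is 1.5 × 7 = 10.5. It is still flat in q.

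**The case against.** The best defence is that the sections can be reconciled. Section 5.1.2 bases efficacy analyses on available data unless otherwise stated, and its zero rule is such a statement, written for exactly this case. Section 7.1.3 says of a skipped item that "otherwise this answer is omitted by design", which makes it a structural zero and not a missing value; 7.4.1 would then cover only questions left unanswered. Section 7.1.3 also expects a total for each subject and visit, with 0 as the least bothersome score, which fits zero-filling far better than a reading in which a symptom-free subject has no total.

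This is probably the intent. But the SAP does not state it, it uses the word imputation for the zero rule, and the reading does not settle the meaning of *answered*. Nor does it help with the Day 1 substitution, which fills genuinely missing values that 7.4.1 says are left alone.

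Two stronger inferences are tempting and should not be drawn.

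- *That the scoring is biased against effective doses.* It is not, on this arithmetic. In the illustration the mean without imputation is the same at every recovery level, so a better arm looks like a worse one. That is masking, not a disadvantage to the better arm.
- *That the Day 1 substitution contradicts the baseline definition.* SAP 5.1.1 defines baseline as the value before test article unless otherwise stated, and 5.1.2 states otherwise. The protocol's Day 1 procedures (9.2.1) list the questionnaire without a time relative to dosing, so a post-dose value is possible but not established.

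**Conclusion.** The conflict is in the text, and one of its permissible readings gives a wrong score. On that reading, subjects with 0 to 3 symptoms lose their bothersomeness total, and totals for 4, 5 and 6 symptoms rise by 75%, 40% and 17% when at least one answered item is above 0. These results follow from the SAP's own rules. The missing percentages and means in the illustration depend on assumed symptom probabilities, on independence and on the assumed bother ratings, and are not a forecast.

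The reach is small. UTISA is an exploratory endpoint (SAP 7.1) and its totals are only described. All seven severity items carry a scored option for an absent symptom, so the skip pattern does not touch the severity total. The frequencies of subjects with all symptoms resolved, no new symptoms and no worsening do not depend on the bothersomeness total. The primary and secondary endpoints and the sample size do not use UTISA. This is a minor clarification worth making, not a threat to the trial's conclusions.

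**What to change.** 1. In SAP 7.1.3, state that a bothersomeness item skipped because the symptom's severity is 'did not have' is scored 0 before the total is formed and counts as answered. State that proration and the four-item minimum apply only to items truly left unanswered.
2. In SAP 7.4.1, replace the no-imputation clause with: *no imputations apart from the scoring rules in 5.1.2 and 7.1.3*. This also reconciles the Day 1 baseline rule.

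Every subject with complete severity answers, and bothersomeness answers for the symptoms present, then has a total: 0 with no symptoms, 4 with four rated 1, 12 with four rated 3. Limiting the Day 1 substitution to pre-dose responses is not a required change.

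The cost is two or three sentences. The change uses the SAP's own zero rule, needs no new data and does not alter trial conduct. It belongs in a SAP amendment before database lock, as SAP 3.5 provides.

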7.14 Permitted Treatments

All other treatments not specified as prohibited are permitted during the study. Subjects requiring additional or alternative antibacterial therapy for their cystitis will be judged as Clinical Failures and test article will be discontinued. Further treatment for their infection is

at the discretion of the investigator or the subject's health care provider and will be considered as a concomitant medication.

Subjects should be encouraged to contact site personnel before starting any new treatment.

For all treatments received by the subject during the study, relevant information must be recorded on the subject's eCRF.

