8.17 Subject Discontinuation or Withdrawal

Reasons why a subject may discontinue or be withdrawn from the study include, but are not limited to, AE, lost to follow up, withdrawal by subject, physician decision, death, and other (specify reason eg, subject non-compliance or study termination by the sponsor). Subjects may voluntarily withdraw from the study for any reason at any time. Subjects are considered withdrawn from the study if they state an intention to withdraw, or fail to return for visits, or become lost to follow up for any other reason. If premature withdrawal from the study occurs for any reason, the investigator should determine the primary reason for a subject's premature withdrawal from the study and record this information on the eCRF.

Subjects who discontinue study treatment should not be considered withdrawn from the study (unless the subject withdraws informed consent). The date and primary reason for

discontinuation of study treatment should be recorded. Subjects who discontinue study treatment prematurely should complete the EOT visit, PTE visit and Final Follow-up Assessment, if possible (see Schedule of Events - [Appendix 1](#)). The site should also collect subject safety information through the Final Follow-up assessment.

Site personnel should also contact the IxRS to register the subject's discontinuation from test article.

For subjects who are lost to follow up, the investigator should show "due diligence" by documenting in the source documents steps taken to contact the subject, eg, dates of telephone calls, registered letters, etc.

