^e Subject assessment of UTI signs and symptoms severity will be collected daily through EOT (including self-completion by subject at home on Days 2, 4 and 6), at PTE and at Final Follow-up via the UTISA questionnaire.

^f Treatments that have been administered within the 7 days prior to the date of signing the ICF or during the Screening phase will be recorded in the eCRF. All medications and significant non-drug therapies administered after the first dose of test article must be recorded in the eCRF.

^g A clean-catch, midstream urine sample should be collected and immediately sent to the local microbiology laboratory for microscopic evaluation and culture. Quantitative urine culture by appropriate methods should be performed using a calibrated loop that would identify bacteria at a lower limit of 10^3 CFU/mL. White blood cell counts should be measured by microscopy from spun or unspun urine or dipstick analysis for leukocyte esterase and nitrites. The statement “or microscopic evaluation for white blood cells” refers to the alternative method to assess for the presence of pyuria (inclusion #4), but the dipstick assessment is required regardless of how inclusion is assessed.

^h Urine isolates that grow $\geq 10^3$ CFU/mL (whether at Baseline or post-Baseline) and are not deemed to be a contaminant as detailed in the Micro Manual, are to be sent from the local lab to the Central Lab for further analysis.

ⁱ A full physical examination will be completed at Screening, thereafter only changes from Screening assessments should be recorded as AEs in the eCRFs.

^j BP and heart rate should be measured within 30 min before, and approximately 1 hour (\pm 15 minutes) after and 3 hours (\pm 15 minutes) after the completion of the first dose on Day 1.

^k Hematology includes coagulation.

^l All subjects will have a local urine or serum pregnancy test at Screening which results will be used to confirm eligibility.

^m All subjects will have blood collected for a serum β -hCG pregnancy test at the Central Laboratory at the Screening and EOT visits.

ⁿ A subject’s AEs and SAEs will be recorded and reported from signing of the ICF to the Final Follow-up assessment.

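### The exploratory UTISA symptom-resolution rates at PTE and FFU have no visible rescue rule, so women who recovered on another antibacterial can count as resolved in their randomized arm

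*SAP*

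**What the plan says.** **UTISA.** SAP 7.1.3 defines the responder summary as "Frequency of subjects with resolution of all symptoms, without occurrence of new symptoms (in comparison to baseline), and no worsening of baseline symptoms", reported by timepoint. Protocol Appendix 1 collects the questionnaire daily through EOT, then "at PTE and at Final Follow-up via the UTISA questionnaire". SAP 7.4.1 plans to present the "Frequency of subjects with resolution of all clinical UTI symptoms, subjects with no worsening symptoms" and the absence of new symptoms, and adds that "Summaries will be based on the available data; no imputations will be applied to missing values". The endpoint table in SAP 7.1 lists UTISA as exploratory, in the ITT, micro-ITT and CE populations.

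**Rescue, for clinical response.** Protocol 7.14: "Subjects requiring additional or alternative antibacterial therapy for their cystitis will be judged as Clinical Failures and test article will be discontinued". SAP 5.1.2 explains that Overall Clinical Response is a worst-case derivation "to accommodate for missing visit assessments and intercurrent events (eg rescue medication at EOT visit", and that similar imputations apply to microbiological response. In SAP Tables 5 and 6, a failure at one visit stays a failure at the next even if the later rating is success.

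**Follow-up after rescue.** Protocol 8.17: "Subjects who discontinue study treatment prematurely should complete the EOT visit, PTE visit and Final" Follow-up assessment where possible. Protocol 9.5.1 and 9.5.2 include UTISA among the procedures at both post-treatment visits and extend those visits to prematurely withdrawn subjects (at FFU, except those who withdraw consent).

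**The concern.** Clinical and microbiological response both have a rule that carries an earlier failure forward. The UTISA resolution frequency has none that can be seen. It is read from the questionnaire at each visit, and women who have been rescued are asked to keep completing it. At PTE and FFU it therefore describes whether symptoms are gone after test article plus any rescue, among women who answered. A reader will tend to take it as the rate at which the test article resolved symptoms.

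UTISA is the trial's only subject-reported efficacy measure, and the primary endpoint is rated by the investigator. The symptom table is likely to be read beside the primary result when doses are compared. The same woman can be a Failure in one table and resolved in the other, with nothing to tell the reader why.

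**Working it through.** **Step 1: follow one subject through the text.** A woman is rated Failure at EOT, starts another antibacterial, attends PTE within its window and reports no symptoms.

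- Overall Clinical Response at PTE is Failure, whatever the PTE rating (SAP Table 5).
- Overall Clinical Response at FFU is Failure (SAP Table 6).
- UTISA resolution at PTE is resolved, because nothing in SAP 7.1.3 or 7.4.1 refers to rescue.
- The CE populations do not remove her. SAP 4.4 keeps failures who received non-study antibiotics for insufficient effect, provided they meet the other criteria.

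The other visible UTISA rules do not address rescue. They cover baseline taken from Day 1 and bothersomeness set to 0 when a symptom is absent (SAP 5.1.2), prorated totals (SAP 7.1.3) and visit windows (SAP 5.1.3).

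**Step 2: inputs for an illustration.** The documents give no UTISA resolution rate and no rescue rate, so there is no planned figure to reproduce.

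- Nitrofurantoin p = 0.82: the design success rate in SAP 3.1.
- Omadacycline p = 0.72: assumed, one 10-point margin (SAP 7.2) lower.
- Resolution on test article without rescue is set equal to clinical success: assumed.
- r, the share of failures rescued and symptom-free by the visit: assumed, shown over a range.

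**Step 3: common r in both arms.** The rate as written is p + (1-p)r. The arm difference is therefore the true difference multiplied by (1-r).

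| r | Nitrofurantoin | Omadacycline | Difference (points) |
|---|---|---|---|
| 0 | 82.0% | 72.0% | -10.0 |
| 0.25 | 0.82 + 0.18×0.25 = 86.5% | 0.72 + 0.28×0.25 = 79.0% | -7.5 |
| 0.50 | 0.82 + 0.18×0.50 = 91.0% | 0.72 + 0.28×0.50 = 86.0% | -5.0 |
| 0.75 | 0.82 + 0.18×0.75 = 95.5% | 0.72 + 0.28×0.75 = 93.0% | -2.5 |

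With 0.82 in both arms and r = 0.50, both rates are 91.0%. The level rises by 9 points and the difference stays 0.

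**Step 4: r differs by arm.**

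- r = 0.5 for nitrofurantoin and 0.9 for omadacycline: 91.0% v 0.72 + 0.28×0.9 = 97.2%, a difference of +6.2 points.
- r = 0.9 and 0.5: 0.82 + 0.18×0.9 = 98.2% v 86.0%, a difference of -12.2 points.

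**Step 5: available data only.** If a share m of failures has no UTISA at the visit, the rate is [p + (1-p)(1-m)r] / [p + (1-p)(1-m)].

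- m = 0.25, r = 0: 0.82/0.955 = 85.9% v 0.72/0.93 = 77.4%, a difference of -8.4 points before rounding.
- m = 0.25, r = 0.50: 0.8875/0.955 = 92.9% v 0.825/0.93 = 88.7%, a difference of -4.2 points.
- If instead only omadacycline successes go missing, at 20% (with r = 0): 0.576/0.856 = 67.3% v 82.0%, a difference of -14.7 points.

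Missingness can thus narrow or widen the gap.

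**Step 6: timing.** At PTE, UTISA and the investigator's rating belong to the same visit (Protocol 9.5.1). A woman first judged a failure and prescribed rescue there gives a pre-rescue answer. At PTE, r cannot exceed the share of failures rescued before that visit; if half were (assumed), r is at most 0.50. FFU, on days 30 to 37, is more exposed.

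**The case against.** The strongest reply is that symptom status at each visit regardless of rescue is a legitimate descriptive summary, and that the primary and FFU clinical endpoints already answer the rescue-as-failure question. That stands as far as it goes, but the SAP does not say that this is the quantity intended, and the table would carry no label to that effect.

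Second, the stakes are small. The visible plan for UTISA is frequencies, shifts and descriptive statistics, with no test, interval or margin. Arm dropping and allocation changes use the investigator's assessment at PTE (Protocol 5.1.1 and 12.7). This stands in full.

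Third, the percentages are illustrative. Clinical success means enough resolution that no further antimicrobial is needed, whereas UTISA asks about seven symptoms, including low back pain and blood in urine, so 0.82 need not be the UTISA rate. This also stands.

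Fourth, parts of SAP 7.4 and 7.5 are not visible. The visible cross-references tie 7.5.1 to the modified micro-ITT populations (SAP 4.6) and 7.5.2 to the primary endpoint (SAP 7.2). That makes a UTISA rescue rule there unlikely but does not exclude it.

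A reader might infer that the UTISA rates necessarily pull the arms together, inflate the weakest dose most, and so wrongly support similarity to nitrofurantoin. The documents do not support that. The direction depends on unequal failure rates with similar recovery after rescue, which steps 3 to 5 show is only one possibility, and the visible plan makes no formal UTISA comparison with nitrofurantoin.

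**Conclusion.** The gap is real and of low priority: a change to consider. In the visible text, the UTISA resolution frequencies at PTE and FFU count post-rescue recovery as resolution in the randomized arm and leave out women without an answer, unlike the plan's own handling of clinical response.

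Rescued recoveries raise the apparent rate of resolution on test article whatever the pattern across arms. The effect on a difference is conditional. With unequal failure rates and a common r, it shrinks by the factor (1-r), from 10 points to 7.5 or 5.0 at r = 0.25 or 0.50. With equal failure rates and a common r, only the level moves. With recovery or missingness that differs by arm, the bias can have either sign. The size rests on assumed values of r and on equating UTISA resolution with clinical success. The primary analysis and the adaptive decisions are untouched.

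**What to change.** In SAP 7.1.3 and 7.4.1:

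1. For resolution of all symptoms at PTE and FFU, count a subject as not resolved if she started an additional antibacterial for cystitis before that UTISA assessment. Take this from the recorded medication start date and reason for therapy (Protocol 8.16), not from the investigator's rating, so that UTISA remains an independent check on the primary endpoint. State how a start on the visit date itself is treated.
2. For ITT and micro-ITT, also show these two rates with all subjects in the arm as denominator and a missing UTISA as not resolved. This need not extend to the daily on-treatment questionnaires, where one skipped home entry would count against a subject.
3. Keep the available-data frequencies, total scores and shifts as descriptive summaries, labelled as including post-rescue data.

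The cost is a few sentences and one added derivation from data already collected, with no new visits or subjects. The reported PTE and FFU resolution rates will be lower, and counting missing answers as not resolved is conservative in level.
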